# 1.3.2 Rationale for Cohort 2 optional oral lead-in and duration of follow-up

Subsequent findings from adult trials with CAB and RPV demonstrated that the LA formulations can be safely administered without an oral lead-in. This has resulted in regulatory approval to administer CAB LA + RPV LA to adults with or without an optional oral lead-in. The FLAIR 124-week Extension Phase data showed that after 24 weeks of treatment, switching to LA treatment with or without an oral lead-in phase had similar safety, tolerability, and efficacy, supporting future evaluation of the simpler direct-to-injection approach (16). As a result of the accumulated safety data which has been generated, the safety of oral CAB and RPV during these four weeks of oral lead-in was not significantly different than at any other time during the FLAIR/ATLAS studies. The FDA and EMA have approved CAB LA + RPV LA to be administered with or without oral lead-in for adults based on the results of the 201584 FLAIR study (7, 17, 18). The FDA has also approved the oral lead-in to be optional for adolescents.

The purpose of Cohort 2 is to incorporate giving study participants the choice to decide between starting with an oral lead-in or initiating a direct to injection regimen with CAB LA and RPV LA (optional oral lead-in) in this component of the study. The FLAIR 124-week Extension Phase data showed that after 24 weeks of treatment, switching to LA treatment with or without an oral lead-in phase had similar safety, tolerability, and efficacy, supporting future evaluation of the simpler direct-to-injection approach (19). As a result of the accumulated safety data generated, the safety of oral CAB and RPV during these four weeks of oral lead-in was not significantly different than at any other time during the FLAIR/ATLAS studies.

Cohort 2a includes an oral lead-in period, while Cohort 2b does not. This decision to dose with or without an oral lead-in will be determined by the study participant, their parent/caregiver, and any consulting healthcare providers, following parental permission and informed assent discussions with the investigator. While Cohort 1 will provide data to support the regulatory approval of CAB/RPV in this population, it is anticipated that Cohort 2 will add to the existing adult data to support the real-world implementation of CAB/RPV where persons living with HIV will be given the choice for an optional oral lead-in.

Cohort 2 will include approximately 48 or 44 weeks of follow-up for Cohort 2a and 2b respectively; as Cohort 2a participants will receive the oral study product, their on-study period will be approximately 4-6 weeks longer than Cohort 2b. This follow-up period will allow for an adequate evaluation of safety and PK in the Cohort 2 participant population without unnecessarily extending the overall duration of the study. Both Cohort 2a and Cohort 2b participants will have the same number of injections over the course of study participation. Cohort 2 study objectives reflect the duration of the study treatment, duration of study follow-up, and timing of study visits.

# 1.3.3 Rationale for staggered enrollment in Cohort 1

There is currently a robust database with CAB and RPV, albeit there are few data on participants below 50 kg in weight, though the MOCHA study evaluates CAB+RPV in adolescents weighing at least 35kg. A staggered enrollment is proposed to allow for a safe and gradual introduction of the CAB LA + RPV LA regimen in early childhood. The largest three weight bands, Weight Bands 1 (35-<40 kg), 2 (25-34.9 kg), and 3 (20-24.9 kg), will be initially opened for enrollment and a Week 12 interim analysis (minimum n=8 dose-evaluable, with at least 2 dose-evaluable participants in Weight Band 3) will be conducted to evaluate CAB LA + RPV LA in these upper weight-bands before opening enrollment to the remaining two weight-bands, Weight Bands 4 (14-19.9 kg) and 5 (10-13.9 kg).

As long as no safety concerns are noted, enrollment in the first three weight bands to open will continue while an ongoing assessment of PK is made.

The priority population in IMPAACT 2036 (two to less than 12 years old) presents a wide range in physiological parameters including BMI and body weight. It is relatively easy to adjust dosing for oral components based on body weight. However, BMI, body composition, and muscle mass among others, may have a considerable impact on drug absorption from the injection site with the long-acting intramuscular route of administration and present some additional challenges when extrapolating to the two to less than 12-year-old population. Changes in absorption from the injection site with LA can significantly alter drug concentrations. Drug absorption from the IM route could, for example, be faster in children than in adults, although the extent may depend on drug formulation, injection volume, injection site etc.

# 1.3.4 Rationale for Cohort 1 interim analyses and the related components of the study design

The first interim analysis will be conducted once a minimum of 8 dose-evaluable participants across Weight Bands, 1, 2, and 3 (with at least 2 participants in Weight Band 3) have completed Week 12. The PK and safety data from this first interim analysis will support the determination of the appropriate frequency and dose of CAB LA + RPV LA for the remaining participants enrolled in Weight Band 1, 2, and 3, and will allow the opening of Weight Bands 4 and 5 for accrual. A second Week 12 interim analysis will be conducted including the safety and PK from participants in Weight Bands 3, 4, and 5 (minimum n=8 dose-evaluable across Weight Bands 3, 4, and 5, with at least 2 dose-evaluable participants in the Weight Band 5) through their Week 12 visit. The PK and safety

data from both Cohort 1 interim analyses will support the determination of the appropriate frequency and dose of CAB LA + RPV LA for remaining participants enrolled in the study.

The proposed single-arm study design is consistent with and responsive to HIV-1 pediatric regulatory guidance from the EU and US, which allows extrapolation of adult efficacy data. The Week 24 safety assessment time point will serve as the primary endpoint for the study. However, safety, acceptability, PK and antiviral activity will continue to be assessed through Week 72 with related study endpoints at Weeks 24, 48 and 72. These data will provide important information on the short term and long term, (through 72 weeks) use of this two-drug injectable ART in children.

# 1.3.5 Rationale for allowing different administration methods for CAB DT and RPV 2.5 mg tablets in Cohort 2a

Some children may prefer to swallow the pediatric formulation tablets (CAB DTs and RPV 2.5 mg tabs) whole. This is an option used for other pediatric formulation tablets (e.g., dolutegravir dispersible tablets SmPC at Tivicay, INN-dolutegravir [europa.eu]) (20). To possibly expand the options of taking the CAB and RPV pediatric formulation tablets, the option to take the tablets swallowed whole with drinking water (direct-to-mouth) will be explored in this study in Cohort 2a and preliminary analysis of the differences of exposure between the routes of administration will be conducted when data emerges.

## 1.3.6 Rationale for social-behavioral assessments, including qualitative in-depth interviews

In the FDA's 2017 guidance document on patient-focused drug development, patient experience data is recommended as critical to "robust, meaningful, sufficiently representative patient input to inform medical product development and regulatory decision making" (21). In the context of this study, the first to evaluate a long-acting injectable regimen for the treatment of HIV-1 in young children, assessments of acceptability (e.g., preferences, likability, satisfaction, costs/benefits and recommendations) and tolerability can provide much needed context for better understanding experiences with the treatment regimen. Furthermore, given the young age of the participant population in this study, collecting acceptability and tolerability from participants alone may not be sufficient or even possible in some cases; as the primary decision-makers around HIV-1 treatment options for their children, the experiences of parents/caregivers of child participants are essential to understand as well.

This study will use a mixed-methods approach to gather participant experience data that includes brief staff-collected questionnaires for parents/caregivers of all participants and for participants who meet age eligibility requirements specified in Section 6.15 as well as semi-structured in-depth interviews (IDIs) with a subset of enrolled parents/caregivers to expand upon the themes explored in the questionnaires. For Cohort 2, qualitative IDIs will also include an exploration of how and why the decision to join Cohort 2a or Cohort 2b was made. Qualitative work is important in populations where experience is limited and there is reason to believe that interests and behaviors could be different than previously studied populations (i.e., adult/adolescents vs. children). In this case, there is a lack of qualitative data on the topic of a long-acting injectable, repeat dose medicine in young children. The caregiver will have tremendous influence on the healthcare of the child, so understanding their interests and the driving force behind their behaviors is key. Such data will also provide nuance to the validity and relevance of the questions asked in the quantitative questionnaires. In addition, by incorporating both quantitative and qualitative components in a single study, we can integrate (mix) findings to address inherent limitations in each of the methodologies when used in isolation.

# 1.4 Hypothesis

- Oral CAB + RPV and injectable CAB LA + RPV LA will achieve pharmacokinetic targets in children living with HIV-1, two to less than 12 years of age.
- Oral CAB + RPV and injectable CAB LA + RPV LA will exhibit acceptable safety profiles in children living with HIV-1, two to less than 12 years of age.

#### 2 OBJECTIVES

All objectives pertain to the study population of virologically suppressed children living with HIV-1, two to less than 12 years of age and weighing ≥10 kgs and <40 kgs.

# 2.1 Primary Objectives: Cohort 1

The primary objectives of this cohort are to:

- **2.1.1** To describe the repeat-dose pharmacokinetics of CAB + RPV (oral and injectable) through Week 24
- **2.1.2** To assess the safety of the oral lead-in of CAB + RPV, and the safety of CAB + RPV (oral and injectable) through Week 24

# 2.2 Secondary Objectives: Cohort 1

The secondary objectives of this cohort are to:

- **2.2.1** To assess the safety of CAB + RPV (oral and injectable) through Week 48 and through Week 72
- **2.2.2** To describe the repeat-dose pharmacokinetics of injectable CAB LA + RPV LA through Weeks 48 and 72
- **2.2.3** To assess the maintenance of viral suppression of CAB + RPV (oral and injectable) through Weeks 24, 48, and 72
- **2.2.4** To evaluate the tolerability and acceptability of injectable CAB LA + RPV LA through Weeks 24, 48, and 72
- **2.2.5** To describe HIV-1 genotypes and phenotypes for children who experience virologic failure during study treatment
- **2.2.6** To assess immunologic activity of CAB + RPV (oral and injectable) through Weeks 24, 48, and 72

# 2.3 Secondary Objectives: Cohort 2

2.3.1 To describe tolerability and acceptability of 48 weeks of CAB + RPV (oral and injectable) and 44 weeks of CAB LA + RPV LA (injectable only)

- **2.3.2** To describe the safety and repeat-dose pharmacokinetics of 48 weeks of CAB + RPV (oral and injectable) or 44 weeks of CAB LA + RPV LA (injectable only)
- **2.3.3** To describe the maintenance of viral suppression and immunologic activity of 48 weeks of CAB + RPV (oral and injectable) or 44 weeks of CAB LA + RPV LA (injectable only)
- **2.3.4** To describe HIV-1 genotypes and phenotypes for children who experience virologic failure during 48 weeks of CAB + RPV (oral and injectable) or during 44 weeks of CAB LA + RPV LA (injectable only)

# 2.4 Other Objectives: Cohorts 1 and 2

The other objectives of this study are

- **2.4.1** To characterize long-term safety and washout PK through 48 weeks after permanent discontinuation of injectable CAB LA + RPV LA
- **2.4.2** To characterize PK of CAB + RPV oral formulations when dispersed in liquid vs. directly ingested (Weight Bands 3, 4 and 5)

# 3 STUDY DESIGN

#### 3.1 Overview

This is a Phase I/II, multicenter, open-label, non-comparative study to evaluate the safety, tolerability, acceptability, and PK of oral CAB and oral RPV followed by long-acting injectable CAB (CAB LA) and long-acting injectable RPV (RPV LA) to propose the weight-band dosing in virologically suppressed children living with HIV-1 aged two to less than 12 years. The study will also assess the long-acting injectable regimen with and without an oral lead-in period in the same study population.

This study will be conducted among up to 90 children weighing ≥10 kgs and <40 kgs, who are virologically suppressed on stable ART. Approximately 90 parents/caregivers of child participants will also enroll to complete tolerability and acceptability assessments (see Section 6.15). In-depth qualitative interviews with a subset of enrolled parents/caregivers will also be conducted as described in Section 3.4. Unless otherwise noted, the term 'participant' will refer to the children enrolled in the study.

Refer to Section 4 for the study eligibility criteria for participants and caregivers, as well as a description of the study recruitment, screening, and enrollment process. Participants and caregivers will be enrolled at selected study sites.

The study will include two discrete cohorts.

Cohort 1 will open to accrual first. In Cohort 1, participants will be enrolled across five weights bands as follows: Weight Band 1 (35-<40kg), Weight Band 2 (25-34.9kg), Weight Band 3 (20-24.9kg), Weight Band 4 (14-19.9kg), and Weight Band 5 (10-13.9kg).

At least 50 evaluable participants (defined in Section 3.2) will be enrolled in Cohort 1. At least 18 evaluable participants will enroll across Weight Bands 1 and 2 and at least 32 evaluable participants will enroll across Weight Bands 3, 4, and 5. Additionally, at least 6 evaluable participants will be enrolled in each of the four highest weight bands (Weight Bands 1, 2, 3, and 4). At least 10 evaluable participants will be enrolled in the lowest weight band (Weight Band 5).

Accrual into Weight Bands 1, 2, and 3 will begin first. Two interim analyses will be conducted in Cohort 1, as further described in Section 3.2, to assess whether any dosing regimen modifications are indicated per weight band. If a dose modification is indicated following the results of either interim analysis, accrual into the relevant weight band(s) will be paused pending the outcome of an SMC review (see Section 3.2). The first interim analysis will also determine the opening of Weight Bands 4 and 5 to accrual. Once Weight Bands 4 and 5 are opened, accrual will continue until all sample size targets within and across weight bands are met and the overall Cohort 1 sample size target is reached. The protocol team will routinely review accrual progress and provide guidance to ensure accrual targets are met. Additional details will also be provided in the study-specific MOP.

At least the first 8 participants across Weight Bands 1 and 2 and the first 8 participants across Weight Bands 3, 4, and 5 will follow the Rich Sampling Schedule for PK evaluations, as outlined in Section 10.3. Once proposed dosing regimens have been evaluated in each weight band and data are sufficient for the PK parameter estimates for both oral and injectable dosing, the protocol team will issue a Memorandum of Operational Instruction switching all participants (currently enrolled and newly enrolling) from the Rich Samling Schedule to the Limited Sampling Schedule (see Section 10.3).

Once enrolled into Cohort 1, participants in each weight band will move through two steps of study participation. In Step 1 (i.e., at study entry), participants will switch from their pre-study ART regimen to daily oral formulations of CAB + RPV for at least four weeks and up to a maximum of six weeks. Participants who meet the eligibility criteria outlined in Section 4.3 and Section 4.4 based on Week 4a visit will transition to Step 2 and receive injectable CAB LA + RPV LA through Week 72. Additional information about transitioning from Step 1 to Step 2 is provided in Section 3.3. Participants who prematurely and permanently discontinue oral CAB + RPV or do not meet eligibility criteria for the injection phase will exit the study 28 days after their last oral study product dosing (See Section 6.3.3). In Step 2, participants will receive injectable CAB LA + RPV LA. Two IM injections, a single injection of CAB LA and a single injection of RPV LA, will be administered at the Week 4b (Step 2 Entry) visit, at the Week 8 visit, and then continuing every four weeks or every eight weeks thereafter, depending on the recommendation of the Week 12 interim analyses (See Section 3.2), with the last injections administered at the Week 72 visit. In both steps, participants will follow the dosing regimens outlined in Section 5.1.

Once Cohort 1 has completed accrual (defined as having enrolled either 50 evaluable participants, as described in Section 3.2, or a maximum of 70 participants overall) and the results of both interim analyses are available and acceptable, Cohort 2 will open to accrual. Cohort 2 will have a planned accrual period of six months, during which up to 20-40 children may enroll (across both Cohort 2a and Cohort 2b, described below). Participants may enroll into either Cohort 2a or 2b, with a minimum accrual target of 4 participants in each. While distribution across weight bands is desirable, there are no weight band requirements for Cohort 2. Should the overall study sample size maximum (approximately 90 children enrolled across all cohorts) not be reached within the sixmonth accrual period for Cohort 2, then Cohort 2 will close to accrual either when the six-month accrual period is completed, or upon reaching the minimum accrual target, whichever is later.

Cohort 2 will consist of two groups, Cohort 2a and Cohort 2b, which will allow participants to choose between a regimen that includes an oral lead-in and one that does not. Participants enrolled in Cohort 2a will progress through two steps of study participation, as described above for Cohort 1. Cohort 2a participants will receive oral CAB + oral RPV (Step 1) through the Week 4b visit, followed by intramuscular injection doses of CAB LA + RPV LA from Week 4b (Step 2 entry) through Week 48, based upon the relevant weight band dosing regimens recommended at the time. Participants enrolled to Cohort 2b will skip the oral lead-in phase and receive both CAB LA + RPV

LA upon entry into the study and continuing through Week 44, based upon the relevant weight-band dosing regimens recommended at the time.

The decision to join Cohort 2a or Cohort 2b will be made by the potential study participant and/or the parent/legal guardian in consultation with the IoR or designee and other healthcare providers, as applicable. This choice will be made as part of the parental permission and informed assent process and must be confirmed prior to study entry; participants may not change their Cohort 2a or Cohort 2b group selection after enrollment.

Section 6.6 provides details for participants who will be followed for an additional 48 weeks on an adjusted follow-up schedule to assess long-term safety and washout PK of the study products, referred to as the LSFU visit schedule. This includes participants who prematurely permanently discontinue study product during the injection phase, participants who discontinue oral or injectable study product due to pregnancy, and participants who complete the injectable study product regimen, but do not wish to continue the CAB LA + RPV LA regimen outside of the study.

## 3.2 Dose-finding and Evaluability: Cohort 1

Cohort 1 will include a dose-finding phase to assess whether any dosing regimen modifications are indicated per weight band; this phase culminates in two separate interim analyses, as described below. Separate terms will be used in the study to describe the participants who will contribute to the dose-finding phase (dose-evaluable) and the participants contributing the accrual targets (evaluable):

- **Dose-evaluable** The term dose-evaluable refers to participants who will be included in the Week 12 dose-finding interim analyses. Dose-evaluable is defined as participants having been treated on the dose being evaluated, and having either (1) completed all treatment through Cohort 1 Week 12 visit or (2) having experienced any of the following:
  - o study drug-related Grade 3+ events (excluding injection-site adverse events), OR
  - o study drug-related SAE, OR
  - o permanently discontinued from treatment due to study drug-related toxicities (regardless of grade) during the dose-finding period.

Participants who receive oral bridging within the first 12 weeks of their study participation will not be considered dose-evaluable.

- **Evaluable** Evaluable participants will be defined as having either (1) completed all treatment through Cohort 1 Week 24, or (2) having experienced any of the following:
  - o study drug-related Grade 3+ events (excluding injection-site adverse events), OR
  - o study drug-related SAE, OR
  - o permanently discontinued from treatment due to study drug-related toxicities (regardless of grade) during these weeks of treatment.

The two interim analyses will be conducted separately:

- The first interim analysis will be based on Weight Bands 1, 2, and 3 to determine whether criteria have been met to open Weight Bands 4 and 5 to accrual, and to determine if any dosing regimen modifications are indicated. It will be conducted once a minimum of 8 dose-evaluable participants have completed the Week 12 visit, with at least 2 dose-evaluable participants enrolled in Weight Band 3 (20-24.9 kg).
- The second interim analysis will be based on Weight Bands from 3, 4, and 5 to determine if any dosing regimen modifications are indicated. It will be conducted once a minimum of 8 dose-evaluable participants across Weight Bands 3, 4, and 5 have completed the week 12 visit (including any participants in Weight Band 3 who contributed data to the first interim analysis), with at least 2 dose-evaluable participants enrolled in Weight Band 5 (10-13.9 kg).

All available PK, safety, viral load, tolerability, and other relevant data will be reviewed by the CMC.

See Section 5.1.2 for more information on dosing regimen modifications. Note that dose modifications will not result in additional interim analyses. If a dose modification is indicated in either cohort, accrual will be paused in the relevant weight band(s) until an SMC review is convened, and the proposed dose modification is approved (see Section 9.5.4). Once accrual is reopened, newly enrolling participants will begin on the modified dose. See Section 9 for further details regarding the review of safety data at interim analyses, study monitoring, the Safety Guidelines, and triggered SMC reviews. See Section 10.3.1 for further details regarding the review of PK data at interim analyses.

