#### 3.3 Transition from Step 1 to Step 2: Cohort 1 and Cohort 2a

Eligibility for each Cohort 1 and Cohort 2a participant will be assessed prior to entry into Step 2 and receipt of injectable CAB LA + RPV LA (See Section 4.3 and Section 4.4). The Week 4b visit serves as the Step 2 Entry visit. This visit should be scheduled to occur as soon as possible after Week 4a laboratory test results are available to minimize the time between the Week 4a visit and initiation of the injectable study products. Clinical assessments conducted at the Week 4b visit, and prior to administering the first injection, will also be used to confirm Step 2 eligibility.

Study visits during Step 2 will be scheduled based on the actual Week 4b visit completion date when the first CAB LA + RPV LA injections are administered.

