## 6.3.3 Week 4a Visit: Step 1 – oral phase for Cohort 1 and Cohort 2a

Participants and their parents/guardians should be reminded to return all oral study product at the Week 4a visit, for the adherence assessment, and to hold administration of the oral product for observed dosing at the clinic. Additional oral study product may be dispensed at this visit if needed to provide coverage until the Week 4b visit.

Data collected through the Week 4a study visit will be assessed to determine eligibility to enter Step 2 and receive injectable CAB LA + RPV LA. Week 4a visit laboratory test results should be reviewed as soon as they are available, for determining Step 2 eligibility and scheduling the Week 4b visit. Abnormal laboratory test result values from the Week 4a visit may be repeated prior to scheduling the Week 4b visit. If laboratory test results confirm Step 2 eligibility, and all other eligibility criteria are met, the Week 4b visit may be scheduled within the target visit window for Step 2 Entry and injectable study product administration, and may be combined with the Week 4a visit. See Section 4.3 and Section 4.4 for Step 2 eligibility criteria.

If participants are ineligible to receive injectable study product in Step 2, they will permanently discontinue oral study product use and complete an Early Termination visit 28 days after their last oral study product dose (see Section 6.6.2).

Cohort 1 an	nd Cohort 2	2a Week 4a Visit Procedures (Step 1 – oral phase)
Behavioral a	nd	Provide adherence counseling
Counseling		Provide contraceptive counseling^
Clinical		Update medical and medications history
(prior to disp		Perform complete physical exam
oral study pr	roduct)	Perform adherence assessment
		Identify/review/update adverse events
Laboratory	Blood	Collect blood for:
		
 
Hematology: CBC (WBC, RBC, hemoglobin, hematocrit, MCV, MCHC) with differential, ANC (absolute neutrophil count), and platelet count
 
Chemistries: Creatinine, eGFR, CK, Direct bilirubin, Total bilirubin, BUN, AST, ALT, Lipase, Albumin
 

	Blood or Urine	Pregnancy test, prior to dispensing oral study product^
Study product		Prescribe and dispense oral study product, if indicated
		Facilitate administration of oral study products (including provision of a meal)

^ For participants of childbearing potential.

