## **Appendix II: Target Visit Dates and Visit Windows**

		ugh Week 72) and COHORT 2A				
Study Visit Name	Target Visit Date	Target Visit Window	Min/Max requirements (from previous IM)			
Week 2	14 days from entry	-7/+6 days from target date	N/A			
Week 4a	28 days from entry	-7/+10 days from the target date	N/A			
Week 4b	As soon as lab results are and no later than 42 days	available from the Week 4a visit from entry	N/A			
Week 5	3 days from Week 4b	-1 day/+4 days from the target	N/A			
Week 6	12 days from Week 4b	date	N/A			
Week 8	28 days from Week 4b	-7 days/+3 days from the target date	minimum of 3 weeks (21 days) and a maximum of 4 weeks and 3 days (31 days) apart, as counted from the previous injection			
Week 9	3 days from Week 8	-1 day/+5 days from the target date	N/A			
Week 12	56 days from Week 4b					
Week 16	84 days from Week 4b	-7 days/+3 days from the target date				
Week 20	112 days from Week 4b	_				
Week 24	140 days from Week 4b					
Week 28	168 days from Week 4b	_				
Week 32	196 days from Week 4b	_				
Week 36	224 days from Week 4b					
Week 40	252 days from Week 4b		minimum of 3 weeks (21 days) and a			
Week 44	280 days from Week 4b		maximum of 5 weeks (35 days) apart, as counted from the previous injection			
Week 48	308 days from Week 4b	-7/+7 days from the target date				
Week 52	336 days from Week 4b					
Week 56	364 days from Week 4b					
Week 60	392 days from Week 4b					
Week 64	420 days from Week 4b					
Week 68	448 days from Week 4b					
Week 72	476 days from Week 4b					

Q8W: COHORT 1 (through Week 72) and COHORT 2A (through Week 48 only)								
Study Visit Name	Target Visit Date	Target Visit Window	Min/Max requirements (from previous IM)					
Week 2	14 days from entry	-7/+6 days from target date	N/A					
Week 4a	28 days from entry	-7/+10 days from target date	N/A					
Week 4b	As soon as lab results are and no later than 42 days	available from the Week 4a visit from entry	N/A					
Week 5	3 days from Week 4b	-1 day/+4 days from the target	N/A					
Week 6	12 days from Week 4b	date	N/A					
Week 8	28 days from Week 4b	-7 days/+3 days from the target date	a minimum of 3 weeks (21 days) and a maximum of 4 weeks and 3 days (31 days) from the Week 4b injection					
Week 9	3 days from Week 8	-1 day/+5 days from the target date	N/A					
Week 12	56 days from Week 4b		N/A					

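### The visit schedule for Week 4b omits the four-week minimum oral lead-in that Section 3.1 requires, so a first injection is schedulable on Days 21-27

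*Protocol*

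**What the plan says.** Section 3.1 of the protocol sets both ends of the oral lead-in for Cohort 1: "daily oral formulations of CAB + RPV for at least four weeks and up to a maximum of six weeks". It then extends the arrangement to Cohort 2a: "Participants enrolled in Cohort 2a will progress through two steps of study participation, as described above for Cohort 1".

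The scheduling text is in Appendix II, to which Section 6.1.1 sends sites for all visit windows. In both the Q4W and the Q8W table for Cohorts 1 and 2a:

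- Week 4a has a target of 28 days from entry and a window from 7 days before to 10 days after it.
- Week 4b has no target day. Its timing begins "As soon as lab results are" available from Week 4a, and its only numerical limit is "no later than 42 days" from entry. The minimum/maximum column is marked not applicable.

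Three other sections bear on the gap between the visits. Section 6.3.3 says that, once results confirm eligibility, Week 4b may be scheduled within its window "and may be combined with the Week 4a visit". Section 3.3 wants Week 4b "as soon as possible after Week 4a laboratory test results are available to minimize the time between the Week 4a visit and initiation" of the injections. Section 6.3.4 repeats the instruction to keep that gap short and requires the Week 4a results to be in hand first. The Step 2 criteria in Sections 4.3 and 4.4 name no minimum number of days on oral drug; criterion 4.3.4 asks for the investigator's judgement that adherence was sufficient.

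**The concern.** The 42-day limit in Appendix II is exactly the six-week ceiling of Section 3.1, so one end of the range was carried into the schedule and the other was not. With Week 4a open from Day 21 and every scheduling instruction pressing for a short gap, the schedule permits injections that Section 3.1 forbids.

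Section 1.3.1 justifies the lead-in as the chance to see acute toxicity while the drug can still be stopped, before a depot dose that cannot be removed, and cites adult trials that used 30 days of oral dosing. Lead-in safety is also a primary objective for Cohort 1 (Section 2.1.2). An early injection shortens that observation and leaves the site with a deviation that the protocol's own table produced. Sites that schedule from different sections would treat children differently.

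**Working it through.** This is visit-window arithmetic, counted in days from entry.

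**Inputs**

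- Lead-in range (Section 3.1): 4 × 7 = 28 days to 6 × 7 = 42 days.
- Week 4a (Appendix II): target Day 28, window -7 to +10 days.
- Week 4b (Appendix II): after the Week 4a results, by Day 42, no lower limit.
- Laboratory turnaround *t*: not given in the protocol. I assume 0 to 7 days, with Week 4b held on the day the results arrive.

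**Reproducing the stated range**

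- Ceiling: 6 × 7 = 42, which matches Appendix II.
- Week 4a window: 28 - 7 = 21 to 28 + 10 = 38, so Days 21-38, which is 18 days.
- Earliest Week 4b = 21 + *t*, which is below 28 whenever *t* is under 7. The floor does not reproduce.

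**Size of the shortfall**

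Shortfall = 28 - (21 + *t*), as a share of 28. The last column counts the Week 4a days *d* for which *d* + *t* < 28.

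| Turnaround *t* (days) | Earliest first injection | Shortfall | Share of 28 days | Week 4a days allowing injection before Day 28 |
|---|---|---|---|---|
| 0 (combined visit) | Day 21 | 7 days | 25.0% | Days 21-27: 7 of 18 |
| 1 | Day 22 | 6 days | 21.4% | Days 21-26: 6 of 18 |
| 3 | Day 24 | 4 days | 14.3% | Days 21-24: 4 of 18 |
| 5 | Day 26 | 2 days | 7.1% | Days 21-22: 2 of 18 |
| 7 | Day 28 | none | 0% | none |

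Day 21 itself needs same-day results, because Section 6.3.4 requires them before Week 4b.

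**With a 28-day floor**

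The permitted first-injection range becomes Days 28-42, as Section 3.1 states. The longest wait that the floor can force after Week 4a is 28 - 21 = 7 days. The present ceiling already permits a gap of 42 - 21 = 21 days.

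**The case against.** The best answer is that nothing in the protocol tells a site to inject before four weeks. Section 3.1 states the minimum, Appendix II is silent on it, and read together they give Days 28-42. On that reading each provision has an innocent purpose. Opening Week 4a on Day 21 lets results come back by Day 28. The combined visit remains usable for Week 4a on Days 28-38 (11 of the 18 days), and keeping the gap short need not mean going below four weeks. Section 6.1.1 also asks for visits close to target, and at the Day 28 target there is no shortfall. Elsewhere the duration is loosely put: Table 5 speaks of roughly four weeks. Section 6.3.4 refers sites to the operations manual for scheduling Week 4b, and that manual, which is not at hand, may restate the floor.

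Much of this stands as a limit on the consequence. A site that applies Section 3.1 will wait, and the full seven-day shortfall needs both the earliest Week 4a day and same-day results. It does not remove the inconsistency, because the operative window table allows what Section 3.1 rules out. The approximate wording in Table 5 describes an estimand and does not override an explicit minimum.

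Two further points are fair. The fix adds no laboratory test before the injection, so the gain is extra days of clinical observation only. For Cohort 2a the safety case is weaker, since Cohort 2b children are injected with no lead-in at all.

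**Conclusion.** The concern holds. Section 3.1 requires 28 to 42 days of oral dosing, while the schedule in Appendix II, together with Sections 3.3, 6.3.3 and 6.3.4, permits a first injection from Day 21. The shortfall is at most 7 days (25%) and disappears once turnaround reaches 7 days. These figures rest on the assumed turnaround. How many children would be affected cannot be estimated from the protocol.

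The practical effect is modest. Week 2 and Week 4a laboratory tests, the history, examination and adverse-event review on the injection day, and the Week 5 laboratory tests about three days after injection all remain. No analysis is shown to be biased, because Step 2 visits are counted from the actual Week 4b date (Section 3.3). The point is worth correcting because the stated observation time on removable drug can be lost on a schedule that looks compliant, and the correction is small.

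**What to change.** In the Week 4b rows of both Appendix II tables for Cohorts 1 and 2a (Q4W and Q8W), and in Section 6.3.4, state that Week 4b takes place as soon as the Week 4a results are available, but not before Day 28 and not after Day 42 from entry. Section 6.3.3 ties the combined visit to the Week 4b window, so the same change bounds that option. The Day 21-38 window for Week 4a can stay.

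The cost is two table rows and one sentence. Some children would wait up to seven more days on oral study drug, which Section 6.3.3 already lets sites dispense at Week 4a. Results from a Day 21 visit could be up to 7 days old at injection because of the floor, well inside the 21 days that the current ceiling permits.
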